9.5.1.2 Primary Estimator

The primary efficacy endpoint, Change from Baseline at Week 6 in the ABC-I score, will be analyzed using MMRM model. The model will include effects for the age group (5 through 12 years old or 13 through 17 years old; categories based on age at screening), region (US or rest of world), treatment group (pimavanserin high dose, pimavanserin low dose, or placebo), visit (Week 1, Week 2, Week 3, Week 4, Week 5, or Week 6), the treatment-by-visit interaction, and the Baseline ABC-I score. An unstructured covariance matrix and Kenward-Roger approximation for the denominator degrees of freedom will be used. The primary treatment comparisons will be based on the difference in least squares means at Week 6 between each pimavanserin dose group and the placebo group using the Full Analysis Set.

A hierarchical testing procedure will be used to control the Type 1 error rate across the two treatment comparisons (pimavanserin high dose vs. placebo and pimavanserin low dose vs. placebo) for the primary endpoint. The hypotheses testing will be conducted in sequential order: 1. pimavanserin high dose versus placebo, 2. pimavanserin low dose versus placebo. If the first comparison fails to reach statistical significance at the 2-sided 0.05 level, the subsequent comparison will be declared as not statistically significant regardless of the associated nominal p-value. The study-wise Type 1 error rate will be maintained at the significance level of 0.05.

In addition to the primary treatment comparisons for the Week 6 timepoint, the treatment groups will also be compared at each of the other timepoints (Weeks 1, 2, 3, 4, and 5) using the same MMRM model described above. These other comparisons will be considered exploratory.

9.5.2 Secondary Endpoint Analyses

Secondary endpoints are the following:

- Change from Baseline at Week 6 in the caregiver-rated ABC subscale scores
 - Stereotypic behavior
 - Lethargy
 - Hyperactivity
 - o Inappropriate speech
- Change from Baseline at Week 6 in the Clinical Global Impression—Severity (CGI-S) of irritability score
- Clinical Global Impression–Improvement (CGI-I) of irritability score at Week 6
- Change from Baseline at Week 6 in the Repetitive Behavior Scale–Revised (RBS-R) scores

Final Version: 1.0

Socialization subscale score

• Change from Baseline at Week 6 in the Vineland Adaptive Behavior Scales (VABS)—

- Change From Baseline at Week 6 in the Caregiver Strain Questionnaire (CGSQ) scores
- Proportion of subjects who have at least 25% reduction from Baseline in the ABC-I subscale score (ABC-I responders) at Week 6
- Proportion of subjects who have CGI-I of irritability score of 1 (very much improved) or 2 (much improved) (CGI-I of irritability responders) at Week 6
- Proportion of subjects who have at least 25% reduction from Baseline in the ABC—Irritability subscale score AND a CGI-I of irritability score of 1 (very much improved) or 2 (much improved) at Week 6

The change from Baseline to each post-Baseline timepoint in the ABC subscale scores (lethargy, stereotypic behavior, hyperactivity, inappropriate speech) and the CGI-S of irritability score will be analyzed using an MMRM model similar to that described above for the primary endpoint, except that the Baseline value of the endpoint being analyzed will be included in the model instead of the Baseline ABC-I subscale score.

The CGI-I of irritability score at each post-Baseline timepoint will be analyzed using an MMRM model. The dependent variable will be the CGI-I of irritability score. The independent variables in the model will include the following: age group, region, treatment group (pimavanserin high dose, pimavanserin low dose, or placebo), visit (Week 1, Week 2, Week 3, Week 4, Week 5, or Week 6), the treatment-by-visit interaction, and the Baseline CGI-S of irritability score.

The change from Baseline to each post-Baseline timepoint in the RBS-R scores, the VABS-Socialization subscale score, and the CGSQ scores will be analyzed using an MMRM model similar to that described above for the primary endpoint, except that the Baseline value of the endpoint being analyzed will be included in the model instead of the Baseline ABC-I subscale score, also the visit variable included in the model will reflect the visits scheduled for the respective endpoints.

The proportion of subjects with ≥25% reduction in the ABC-I subscale score, the proportion of subjects with a CGI-I of irritability score of 1 or 2, and the proportion of subjects with ≥25% reduction in the ABC-I subscale score AND a CGI-I of irritability score of 1 or 2 will be summarized at each post-Baseline timepoint. The proportions will be compared between each pimavanserin dose group and the placebo group using Cochran-Mantel-Haenszel test stratified by age group and region.

Final Version: 1.0

9.5.3 Safety Endpoints

Safety results will be summarized by treatment group using descriptive statistics. No formal statistical testing will be performed for any of the safety endpoints.

9.5.3.1 Treatment-emergent Adverse Events

All AEs will be coded using the Medical Dictionary for Regulatory Activities (MedDRA) coding dictionary. All AEs will be listed and treatment-emergent adverse events (TEAEs) will be summarized by system organ class and preferred term. A TEAE is defined as an AE that started after first study dose administration and no later than last study dose date + 30 days. TEAEs leading to discontinuation, TEAEs related to study drug, TEAEs by maximum severity, fatal TEAEs, serious TEAEs, and serious TEAEs related to study drug will also be summarized.

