6.4.7 Somnolence

Medical history of somnolence will be recorded at screening. At each study visit, the investigator should query the caregiver for occurrences of somnolence from the last visit. An occurrence of somnolence should be reported as an adverse event. If the caregiver reports an occurrence of somnolence, the investigator should ask the "somnolence adverse event" questions in Appendix H.

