7.2.3 Duration

The start and stop dates for AEs will be recorded using the following criteria:

- Start: Date of the first episode of the AE or date of worsening in severity
- **Stop:** Date when AE recovered or resolved, recovered or resolved with sequelae, or worsened in severity

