7.2.4 Frequency

The frequency of the AE should be indicated according to the following definitions:

- Single: Experienced once, without recurrence at same severity
- **Recurrent:** More than one discrete episode with the same severity

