7.3 Time Period and Frequency for Event Assessment and Follow-up

Adverse events will be recorded from the time informed consent is obtained through the study safety follow-up period. If an AE is ongoing at the end of the study safety follow-up period, every reasonable attempt should be made to follow and appropriately treat the subject until the AE resolves or until the Investigator deems the AE to be chronic or stable. If the subject rolls over into the open-label study, any ongoing AEs will be followed in the open-label study.

In the event that a subject discontinues from the study and has an ongoing AE at the time of discontinuation (Section 4.5.1), the subject should be followed and appropriately treated until the AE resolves or until the Investigator deems the AE to be chronic or stable. If a subject withdraws from the study because of an AE, no additional assessments may be performed (Section 4.4).

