14.1 Adverse Events

All Adverse events (AEs) will be coded using MedDRA version 24.0 or higher.

An AE (classified by preferred term) will be considered a treatment-emergent AE (TEAE) if it starts after the first study dose administration and no later than last study dose date + 30 days. AEs reported on Day 1 based on Baseline (pre-dose) findings (e.g. clinically significantly abnormal vital signs, laboratory test results, or electrocardiogram parameters) will not be considered as TEAEs.

The event counts and the number and percentage of subjects reporting TEAEs in each treatment group, and the two pimavanserin groups combined will be tabulated by SOC and preferred term; and, by SOC, preferred term, and maximum severity. If more than one AE occurs with the same preferred term for the same subject, the subject will be counted only once for that preferred term using the most severe and more related occurrence for the summarization by severity and by relationship to study drug, respectively. The display in these tables will be sorted alphabetically by SOC, and then by frequency of the two pimavanserin groups combined within each SOC.

The event counts and the number and percentage of subjects with any TEAEs will also be tabulated by preferred term without SOCs within each treatment group and sorted by frequency of the two pimavanserin groups combined.

The incidence of most frequently reported (preferred terms reported by $\geq 5\%$ of subjects in any treatment group) TEAEs, TEAEs leading to discontinuation, TEAEs related to study drug, TEAEs by maximum severity, fatal TEAEs (i.e., events that cause death), serious TEAEs, and serious TEAEs related to study drug, will be summarized by SOC, preferred term, and treatment group. In addition, TEAEs by SOC, preferred term, and stimulant use will be summarized.

Version 3.0

29 July 2024

The relationship of selected AEs to COVID-19 will be assessed as detailed in the GSD and provided in the listing. Additional summaries of relationship to COVID-19 may be provided.

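### A start-date-only TEAE rule can leave out on-drug recurrence or progression, at unchanged severity, of an AE first recorded before dosing

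*Protocol*

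**What the plan says.** Treatment emergence is decided by the AE start date in both documents. Protocol 9.5.3.1: "A TEAE is defined as an AE that started after first study dose administration", with an outer limit of 30 days after the last dose. SAP 14.1 counts an AE as treatment-emergent "if it starts after the first study dose administration and no later than last study dose date + 30 days". Neither has a clause for an event that began before dosing and then returned or progressed.

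The recording rules fix what the start date is. Protocol 7.2.3 sets it as "Date of the first episode of the AE or date of worsening in severity". The stop date is when the AE resolves or worsens. Protocol 7.2.4 offers two frequency labels, and *Recurrent* means "More than one discrete episode with the same severity".

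Collection begins before dosing. Protocol 7.3: "Adverse events will be recorded from the time informed consent is obtained through the study safety follow-up period". Screening lasts 3-28 days and can be extended by 7. Table S-1 has syncope and somnolence assessed at Screening and Baseline as well as on treatment. Protocol 6.4.7 adds: "An occurrence of somnolence should be reported as an adverse event"; 6.4.6 says the same of syncope. SAP 14.6 sends on-study syncope and somnolence to the TEAE summaries.

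The outputs at issue are the SAP 14.1 tables, which give "The event counts and the number and percentage of subjects reporting TEAEs in each treatment group", and the tables of serious TEAEs, related TEAEs and TEAEs leading to discontinuation.

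**The concern.** A drug can do harm by making an existing event come back, come more often or become serious, as well as by causing a new one. A start-date rule sees the last three only if something gives the event a new start date, and here only a worse severity grade clearly does so. Seriousness is classified separately from severity (Protocol 7.1.2), so an AE can become serious with no change of grade.

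The TEAE tables are the only planned comparison of AEs by arm. If the drug provokes recurrence, more cases are lost from the active arms than from placebo, and the difference shrinks. Sites that record the same history differently would also feed the same table with different counts.

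**Working it through.** There is no stated figure to reproduce, so the first step is to trace the rules. Take an AE first recorded between consent and first dose:

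| What happens on drug | Start date under 7.2.3 and 7.2.4 | TEAE? |
|---|---|---|
| Returns at the same severity, kept on one *Recurrent* record | Pre-dose | No |
| Resolves, returns at the same severity, entered as a new record | Post-dose | Yes |
| Returns or continues at a worse grade | Date of worsening | Yes |
| Becomes more frequent at the same grade, one record | Pre-dose | No |
| Ongoing at first dose; becomes serious or leads to discontinuation at the same grade | Pre-dose | No |

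The first two rows are the same clinical history with opposite results, and the documents do not choose between them. The *Recurrent* label favours one record: discrete episodes end between occurrences, so if every resolution closed the record for good, the label would have almost nothing to describe. The stop-date rule favours a new record. The last row does not depend on that choice, because nothing in 7.2.3 gives a new start date for seriousness or discontinuation.

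The SAP's default for unclear onset (5.4.3) does not help: it applies only when dates are missing or incomplete.

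**Size, on assumed rates.** Let *p* be the share of children with the preferred term recorded before dosing, the same in each arm. Let *r* be the share of those in whom it recurs on treatment, always at the same severity and kept on the old record. Let *a* be the incidence in children without a pre-dose record.

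- True risk = (1 − p)a + pr
- Counted risk = (1 − p)a
- Children lost per arm = 76 × p × r
- Understatement of the risk difference = p × (r on drug − r on placebo)

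The 76 per arm is from Protocol 9.3. The values of *p* and *r* are assumptions.

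| p | Lost per active arm, r = 60% | Lost on placebo, r = 30% | Understatement, 60% v 30% | Understatement, 50% v 40% |
|---|---|---|---|---|
| 2% | 76 × 0.02 × 0.6 = 0.9 | 0.5 | 0.6 points | 0.2 points |
| 5% | 76 × 0.05 × 0.6 = 2.3 | 1.1 | 1.5 points | 0.5 points |
| 10% | 76 × 0.10 × 0.6 = 4.6 | 2.3 | 3.0 points | 1.0 point |

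For example, with *p* = 10%, *a* = 12% on drug and 5% on placebo (also assumed), and 60% against 30% recurrence, the true difference is 0.9 × 7 + 0.1 × 30 = 9.3 points. The table would show 0.9 × 7 = 6.3.

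If half of the recurrences in each arm worsened, they would count, and the losses and understatements would halve (0.1-1.5 points overall).

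**Event counts.** Under the same rules, one episode that worsens twice makes three records, while ten same-severity episodes can make one.

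**The case against.** The strongest objection is that the one-record reading is an inference. No section says that a post-dose episode must stay on a Screening record, and the stop-date rule lets a site close the old AE and open a new one, which would be a TEAE. The eCRF instructions that might settle this are not in the documents. This stands. A reader might infer that such episodes are never counted, and the documents do not support that.

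Several provisions limit the effect:

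- A worse grade gets a new start date. Grades are defined by interference with everyday activities (7.2.1), so a large rise in frequency may raise the grade.
- Protocol 7.1.1 deliberately leaves out stable or intermittent chronic conditions that do not worsen. That does not cover a new condition arising after consent, which 6.1.2 makes an AE.
- A reader might infer that syncope and somnolence appear only as TEAEs. SAP 14.6 also lists both assessments by visit. Its sentence sending them to the TEAE summaries does not, however, change the start-date test in 14.1. If it is meant to count every on-drug occurrence, the two sections conflict and need reconciling.
- A reader might infer that the affected events vanish. The all-AE listing includes non-emergent events with their frequency, the SAE and fatal AE listings are not limited to TEAEs, and SAP Section 6 tabulates discontinuation by primary reason and arm. Listings, though, are not comparisons by arm.
- A reader might infer that split records inflate incidence. They do not: SAP 14.1 counts each child once per preferred term. Only the event-count column is affected.

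The rates are assumed, safety is descriptive, and the effect is small beside sampling error. At 12% against 5% with 76 per arm, the standard error of the difference is √(0.12 × 0.88/76 + 0.05 × 0.95/76) = 4.5 points. That is fair, but the omission is systematic: if the drug provokes recurrence, it always lowers the difference.

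**Conclusion.** The concern holds in this form. On-drug recurrence, increased frequency, or progression to serious or to discontinuation, at unchanged severity, of an AE first recorded before dosing can be left out of the TEAE summaries. This follows from the stated start-date rule, not only from a missing detail. For recurrence after resolution, the outcome depends on a recording choice that the documents leave open and that can differ by site.

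The true size is unknown. The 0.2-3.0 points rest on 2-10% of children having a pre-dose record, on the two assumed pairs of recurrence rates, and on every recurrence being at the same severity and kept on the old record. The direction also rests on recurrence being commoner on drug; if it were commoner on placebo, the bias would reverse. The rule should be changed, because the remedy is cheap and these tables carry the AE comparison.

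**What to change.** - In Protocol 9.5.3.1 and SAP 14.1, define a TEAE as an AE that, after the first dose and within 30 days of the last, starts, recurs after resolution, or worsens in severity, frequency or seriousness.
- In Protocol 7.2.3, 7.2.4 and the eCRF guide, require the first post-dose episode to open a new record, so that no record spans episodes on both sides of the first dose. Capture the date of any increase in frequency or seriousness; otherwise the flag cannot be derived.
- As a minor addition, state in SAP 14.1 that event counts merge contiguous records of one preferred term that were split only for worsening.

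An AE that leads to discontinuation with no change in severity, frequency or seriousness would still fall outside this definition. The disposition table remains its by-arm record.

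The cost is a wording amendment to the protocol, SAP and eCRF guide, with the protocol change submitted to the IRB/EC as Protocol 10.7 requires. Records already entered may not be easy to re-split. Some background recurrences will be counted in every arm, and the placebo column shows that rate. Visits, treatment and the primary analysis are untouched.

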9.5.3.2 Vital Signs, Weight, and Body Mass Index

The vital signs, body weight, and BMI at Baseline and each post-Baseline timepoint will be summarized by treatment group. Change from Baseline values at each post-Baseline timepoint will also be summarized.

The number and percentage of subjects with changes from Baseline (increases and decreases separately) in body weight of 7% or more will also be provided.

9.5.3.3 12-lead Electrocardiograms

The measurement values of ECG parameters at Baseline and each post-Baseline timepoint will be summarized by treatment group. Change from Baseline values at each post-Baseline timepoint will also be summarized.

Categorical analyses will be conducted on the incidence of subjects with prolonged QTc intervals and changes in QTc intervals in accordance with ICH guidelines and based on the FDA E14 Guidance Document.

9.5.3.4 Physical Examination Results

The results of the physical examinations at each visit will be tabulated by treatment group.

9.5.3.5 Clinical Laboratory Tests and Hormonal Assessments

The serum clinical chemistry, hematology, urinalysis and hormonal assessment results at Baseline and each post-Baseline timepoint will be summarized by treatment group. Change from Baseline values at each post-Baseline timepoint will also be summarized.

The number and percentage of subjects with potentially clinically important post-baseline laboratory values will be summarized by treatment group for selected parameters. The criteria

for potentially clinically important values are presented in Appendix C, Appendix D, and Appendix F.

9.5.3.6 Columbia-Suicide Severity Rating Scale

For the C-SSRS, the number and percentage of subjects with suicidal ideation or suicidal behavior during the study will be tabulated.

9.5.4 Pharmacokinetic and Pharmacokinetic/Pharmacodynamic Analyses

Plasma concentration data for pimavanserin and its metabolite (AC-279) will be listed and summarized using standard summary statistics.

If data allow, population PK and PK/PD analyses will be performed to further characterize the PK profile and exposure response relationship of pimavanserin and its metabolite using measures of safety, and efficacy parameters. The results of population PK and PK/PD modeling will be presented in a separate report. Pimavanserin plasma concentration data will remain blinded until the unblinding of the clinical database at the end of the study.

9.5.5 Subgroup Analyses

Selected analyses will be performed in age subgroups (5 through 12 years old or 13 through 17 years old; categories based on age at screening). Additional subgroup analyses may be specified in the SAP.

9.6 Interim Analyses

No interim analyses are planned for this study.

9.7 Data and Safety Monitoring Board

An independent data and safety monitoring board (DSMB) will review interim safety data, including data on AEs, SAEs and safety laboratory data. The DSMB will be independent of the Sponsor and the Investigators and will be empowered to recommend stopping the study due to safety concerns. The membership, activities, responsibilities, and frequency of meetings will be described separately in the DSMB charter.

9.8 Measures to Minimize Bias

Subjects will be stratified by age group (5- through 12-year-olds or 13- through 17-year-olds) and region (US or rest of world). Within each stratum, eligible subjects will be randomized

Final Version: 1.0

treatment groups.

into one of three treatment groups (pimavanserin high dose, pimavanserin low dose, or placebo) in a 1:1:1 ratio using an interactive response technology (IRT) system. The assignments will be based on a pre-generated permuted-block randomization schedule. Blinding will be assured by restricting access of Investigators and Sponsor personnel and/or designee to the treatment codes, and providing identical capsules and packaging for the three

9.9 Breaking the Study Blind/Subject Code

For the final analysis, the treatment codes for all subjects will be released to the Sponsor after all subjects have completed the study and the clinical database is locked.

For DSMB safety reviews, the treatment codes will be released to an independent statistical group to produce unblinded statistical outputs. The Sponsor and the Investigators will remain blinded.

In case of an emergency, the Investigator has the sole responsibility for determining if unblinding of a participants' intervention assignment is warranted. Participant safety must always be the first consideration in making such a determination. If the Investigator decides that unblinding is warranted, the Investigator should make every effort to contact the sponsor prior to unblinding a participant's intervention assignment unless this could delay emergency treatment of the participant. If a participant's intervention assignment is unblinded, the sponsor must be notified within 24 hours after breaking the blind.

If pregnancy occurs during the study, the pregnant subject should be withdrawn and unblinded so that counseling may be offered based on whether the fetus was exposed to the active drug or placebo.

10 STUDY MANAGEMENT AND DATA COLLECTION

10.1 Data Collection and Management Responsibilities

All documents required for the conduct of the study as specified in the ICH GCP guidelines will be maintained by the Investigator in an orderly manner and made available for monitoring and/or auditing by the Sponsor and regulatory authorities.

The Investigator and institution must permit authorized representatives of the Sponsor or designees (including monitors and auditors), regulatory authorities (including inspectors), and the IRB/EC direct access to source documents (such as original medical records) as allowed by local regulations. Direct access includes permission to examine, analyze, verify, and reproduce any records and reports that are needed for the evaluation of the study either in person or through remote video/electronic medium (such as email), if applicable. The

Final Version: 1.0

Final Version: 1.0 Clinical Study Protocol Amendment 4 Date: 21 December 2022

Investigator must ensure the reliability and availability of source documents from which the information on the eCRF was derived.

